5.4 Orientation and Screening Phase – Visit 93 and 93a

Cigarette smokers will be screened for eligibility with a brief telephone screener. Eligibility criteria will be aimed towards being inclusionary to ensure generalizability of results to a broader population of smokers. If subjects meet the initial telephone screening eligibility criteria for the study, they will be asked to participate in a more thorough screening via a virtual remote visit using telehealth technology.

Orientation: The purpose of the orientation is to inform the subjects about the study protocol. The Researcher will review the study via telehealth technology with a PowerPoint detailing the study purpose, procedures and risks. The subject is provided a copy of the consent form and HIPPA for review. After the subject has been able to ask questions and receive answers and show comprehension, the consent form and HIPPA will be electronically signed or paper copies mailed back to the Researcher. Signed copies will be provided to the subject at their first brief clinic or curbside visit.

Screening: After obtaining informed consent, basic information and screening questionnaires will be completed to further screen for eligibility.

93. Screening Procedures (see Table of Procedures page 45):

A. *Physiological Measures:*

- 1) Measures will be taken during the brief in-person visit 93a (see below).

B. *Surveys – link sent to participant to complete REDCap based survey:*

Screening forms

- 1) Demographics (including items needed for Masonic Cancer Center registration).

- 2) Brief Medical History Questionnaire to assess current diagnoses, symptoms and past health problems including psychiatric and substance abuse and medication use.
 - a. Concomitant Medication: Current use and use within the prior 30 days.
 - b. Date of last menstrual period and length of cycle will be acquired to assess pregnancy status.
- 3) Patient Health Questionnaire (PHQ/Prime-MD) will be used to assess current symptoms of depression and anxiety. BDI-II and or GAD7 will be administered for clinician to review if positive for depression or anxiety.
- 4) Contemplation Ladder to assess readiness of smoking cessation.
- 5) NIAAA Alcohol Use Questionnaire (12 month version)
- 6) Nicotine Dependence Questionnaire
- 7) Drug Use Questionnaire (1 month version)

C. *Interviews - Research Assistant interviews participant and enters directly into REDCap (except Identification Form):*

- 1) Tobacco Use History and Nicotine Exposure Questionnaire
- 2) Brief Medical History Follow-up form (completed as needed by study staff to further assess current diagnoses, symptoms or past health problems).
- 3) Tobacco Use 7 Day Followback Form for cigarettes per day, alcohol and marijuana
- 4) COVID-19 Related Questions
- 5) An Identification Form: includes name, address, email, phone number, age and date of birth. This information will be stored separately from any other study data and in a password protected database. This information will not be shared with any other study investigators.
- 6) End of Visit Evaluation

After the telehealth visit, medical review will be conducted by the licensed medical professional and eligibility criteria will be confirmed. If eligibility criteria appear to be met, the participant will be enrolled in the Daily Interactive Text Response (ITR) for data collection via REDCap (described below). If the subject shows compliance with providing the daily ITR data for 5 days, they will attend a brief, in-person visit to complete the screening.

93a In-Person Screen

Physiological Measures:

Prior to the appointment, the COVID Assessment will be completed via phone call. The vitals and carbon monoxide (CO) measures will be taken during the in-person screening visit (93a) using the monitors that will be provided for home use. The subject will receive training on use of the devices and staff will observe the procedure to verify accurate technique and assess competence.

- 1) Height and weight
- 2) Carbon monoxide will be collected using iCO Smokerlyzer, a portable carbon monoxide monitor that can be used at home with a smartphone.
- 3) Blood pressure and heart rate is assessed with the at home monitor provided.

- 4) A spot urine sample will be collected for a pregnancy test [hCG detection] for female participants of childbearing potential to confirm eligibility.
- 5) Participants may be asked to provide 3 of their usual brand cigarettes for ventilation testing.

If the carbon monoxide level, blood pressure and heart rate are within the guidelines, the participant will be considered eligible to enroll. If the CO is below 8ppm, a nicotine check strip may be used to verify regular smoking status.

In addition, biological sample collection supplies and handouts will be provided.

Daily Interactive Text Response (ITR) System and Data Management

At the Screening visit (93), eligible subjects will be trained to use the Daily Text (ITR) system. The ITR system uses a stand-alone REDCap project, in conjunction with Twilio (REDCap approved service provider) to send automatic survey invitations to the participant's phone via a text message. Participants will receive a text message each day throughout the study with a unique link to the REDCap survey. The survey will ask for the previous day's number of cigarettes (both study and non-study cigarettes), use of any other tobacco or nicotine products, marijuana and alcoholic drinks.

To be enrolled in the recording system, research staff must enter subject initials, telephone number, subject identifier and start dates into the HIPAA compliant REDCap project. Identifying information (initials and telephone numbers) will be marked as identifiers and not allowed to be extracted with the data by the Bioinformatics group.

Any missing data due to incomplete or entry errors (e.g., subject entered 88 study cigarettes rather than 8 study cigarettes) will be reviewed at the next visit via the Timeline Follow-back method and compiled in the ITR Review Form. This data will be integrated into the ITR as revised data. The original subject entered data will also be retained in the ITR database.

5.5 Phase 1: Baseline Smoking Usual Brand

During Phase 1, (Screening Visit 93a through Visit 92), eligible subjects will purchase their own cigarettes and smoke their preferred brand as usual. Data will be collected during a telehealth visit and biological sample for biomarker analysis will be collected at the brief clinic or curbside visit (see below).

Procedures for Baseline 1 Telehealth Visit (92)

A. Physiological Measures and Biomarker Samples

- 1) Vital signs (blood pressure, heart rate) will be obtained while conducting the telehealth visit
- 2) Carbon monoxide level will be obtained while conducting the telehealth visit.

- 3) Biological sample collection to assess for nicotine and carcinogen metabolites. A first void urine sample will be collected the morning of the visit and saliva will be collected during the telehealth visit. Samples will be dropped off at the brief clinic or curbside visit.

B. Surveys – link sent to participant to complete REDCap based survey:

Biomarker Modifier Questionnaires:

- 1) Environmental Tobacco Smoke Questionnaire

Subjective Outcome Measures:

- 1) Minnesota Nicotine Withdrawal Scale(MNWS)
- 2) Questionnaire of Smoking Urges-Brief Scale – Usual Brand (QSU)
- 3) Respiratory and Global Health Questionnaire
- 4) Modified Cigarette Evaluation Scale – Usual Brand
- 5) Perceived Health Risk
- 6) Cigarette Purchase Task – Usual Brand
- 7) Duke Sensory Questionnaire – Usual Brand
- 8) BDI-II and or GAD7 will be administered for clinician to review if monitored for depression or anxiety.
- 9) Tobacco Policy Support Questionnaire

C. Interviews - Research Assistant interviews participant and enters directly into REDCap:

- 1) COVID-19 Assessment
- 2) Health Changes and Menstrual Cycle Questionnaire
- 3) Adverse Events
- 4) Concomitant Medications
- 5) Daily ITR Review form (follow-up on missing and unusual reports)
- 6) Timeline Follow-back Questionnaire (since last visit)
- 7) Intention to Quit
- 8) Drug accountability: Complete Dispensing Logs for study cigarettes to be dispensed at brief clinic or curbside visit
- 9) Study Compliance Review
- 10) End of Visit Evaluation

Dispensing Study Product:

At the brief in-person clinic or curbside visit, the participant will be provided the ventilated study cigarettes. The subject will receive instruction on how to track the use of their study cigarettes for the Daily ITR. The subject will be allocated 150% of their baseline usual brand cigarettes per day. Allocating an additional 50% will allow for compensatory smoking behavior and provide a cushion for possible late visits. A nominal amount of money for each unused pack of cigarettes that are returned will be provided in order to disincentivize wasteful use of cigarettes (sharing with friends, hoarding cigarettes). Subjects who return unopened packs of their study cigarettes will receive a \$2 credit per pack that will be paid out at the follow-up visit, with a max credit up to \$30.

5.6 Phase 2: Adaptation to Ventilated Study Cigarette

During Phase 2 (baseline 92 to randomization visit 00), eligible subjects will be provided study ventilated cigarettes. Subjects will be instructed to continue to report on daily intake of tobacco and nicotine products, alcohol and marijuana in the ITR. Data will be collected during telehealth visits and biological samples for biomarker analysis collected at the brief clinic or curbside visit.

Procedures for Visit Telehealth Visit (Visit 91)

A. Physiological Measures:

- 1) CO level will be measured while conducting the telehealth visit.
- 2) Vitals signs (blood pressure, heart rate) will be obtained while conducting the telehealth visit.

B. Surveys – link sent to participant to complete REDCap based survey:

Subjective Outcome Measures:

- 1) Minnesota Nicotine Withdrawal Scale(MNWS)
- 2) Questionnaire of Smoking Urges-brief scale - Study Cigarette (QSU)
- 3) Modified Cigarette Evaluation Scale – Study Cigarettes
- 4) Respiratory Symptoms and Global Health Questionnaire
- 5) Duke Sensory Questionnaire – Study Cigarettes
- 6) BDI-II and or GAD7 will be administered for clinician to review if monitored for depression or anxiety.

C. Interviews - Research Assistant interviews participant and enters directly into REDCap:

- 1) COVID-19 Assessment
- 2) Health Changes and Menstrual Cycle Questionnaire
- 3) Adverse Events
- 4) Concomitant Medications
- 5) Daily IVR Call Review (follow-up on missing and unusual reports)
- 6) Timeline Follow Back Questionnaire
- 7) Intention to Quit
- 8) Drug accountability: Complete Dispensing Logs
- 9) Compliance Review
- 10) End of Visit Evaluation.

Supplies, sample collection containers and handouts will be provided to the participant at the Baseline 91 brief clinic or curbside visit for collection of cigarette butts, urine, saliva and blood spots for the Week 0 baseline sample collection. Participants will be asked to collect cigarette butts 24 hours prior to Visit 00.

Procedures for Visit 2 Telehealth Visit (Visit 00)

At the second Baseline visit (00), subjects will be informed that they have been randomized to either ventilated or unventilated study cigarettes. Subjects will complete several measures and provide biological samples for biomarker analysis as described below.

A. Physiological Measures and Biomarker Samples:

- 1) Vitals signs (blood pressure, heart rate) will be obtained while conducting the telehealth visit.
- 2) Carbon monoxide level will be obtained while conducting the telehealth visit.
- 3) Biological sample collection for analysis of nicotine and carcinogen metabolites will be collected prior to (first void urine sample) or at the telehealth visit (saliva and possibly blood spots) and then dropped off at the brief clinic or curbside visit. Oral cells will be collected during the telehealth, in-person curbside or clinic visit. Subjects will be instructed to brush teeth prior to the collection.
- 4) Review Cigarette Butt Collection: The 24-hour collection of cigarette butts prior to this visit will be reviewed and dropped off at brief clinic or curbside visit. These spent filters will be analyzed for cigarette butt staining to inform intensity of smoking behavior.

B. Surveys – link sent to participant to complete REDCap based survey:

Biomarker Modifier Questionnaires:

- 1) Environmental Tobacco Smoke Questionnaire

Subjective Outcome Measures:

- 1) Minnesota Nicotine Withdrawal Scale(MWSC)
- 2) Questionnaire of Smoking Urges-Brief Scale – Study Cigarette (QSU)
- 3) Respiratory Symptoms and Global Health Questionnaire
- 4) Modified Cigarette Evaluation Scale – Study Cigarette
- 5) Perceived Health Risk
- 6) Cigarette Purchase Task – Study Cigarette
- 7) Nicotine Dependence Questionnaire
- 8) Duke Sensory Questionnaire – Study Cigarette
- 9) BDI-II and or GAD7 will be administered for clinician to review if monitored for depression or anxiety.

C. Interviews - Research Assistant interviews participant and enters directly into REDCap:

- 1) COVID-19 Assessment
- 2) Health Changes and Menstrual Cycle Questionnaire
- 3) Adverse Events
- 4) Concomitant Medications
- 5) Daily ITR Review (follow-up on missing and unusual reports)
- 6) Timeline Follow-back Questionnaire (since last visit)

- 7) Randomization to either ventilated or unventilated cigarettes - Read appropriate script
- 8) Intention to Quit
- 9) Product Accountability Log
- 10) Compliance Review
- 11) End of Visit Evaluation

Dispensing Study Product:

At the brief clinic or curbside visit, the participant will be provided their randomized study cigarettes (ventilated or unventilated). The subject will continue to be allocated 150% of their baseline cigarettes per day and receive a \$2 credit per pack for each unused pack of cigarettes that are returned in order to disincentivize wasteful use of cigarettes (sharing with friends, hoarding cigarettes; max credit up to \$30).

5.7 Phase 3: Assigned Study Cigarette Phase:

Subjects will be smoking the assigned ventilated or unventilated study cigarettes. Subjects will be instructed to continue to report on daily intake of tobacco and nicotine products, alcohol and marijuana in the ITR. In addition, measures as described in the Table of Procedures will be collected. At the Week 3 and 6 visits, biological samples will be collected. Study cigarettes, supplies, collection containers and handouts are dispensed prior to the respective collection weeks during brief clinic or curbside visits. Additionally, cigarette butts will be collected 24 hours prior to Week 3 and 6 visits.

Procedures for Telehealth Weeks 1, 2, 4 and 5

A. Physiological Measures:

- 1) Vital signs (blood pressure, heart rate) will be obtained while conducting the telehealth visit.
- 2) Carbon monoxide level will be obtained while conducting the telehealth visit.

B. Surveys – link sent to participant to complete REDCap based survey:

Subjective Outcome Measures:

- 1) Minnesota Nicotine Withdrawal Scale (MNWS)
- 2) Questionnaire of Smoking Urges-Brief Scale – Study Cigarette (QSU)
- 3) Respiratory Symptoms and Global Health Questionnaire
- 4) Modified Cigarette Evaluation Scale (Week 1 only) – Study Cigarette
- 5) Perceived Health Risk (Week 1 only)
- 6) Duke Sensory Questionnaire (Week 1 only) – Study Cigarette
- 7) BDI-II and or GAD7 will be administered for clinician to review if monitored for depression or anxiety.

C. Interviews - Research Assistant interviews participant and enters directly into REDCap:

- 1) COVID-19 Assessment

- 2) Health Changes and Menstrual Cycle Questionnaire
- 3) Adverse Events
- 4) Concomitant Medications
- 5) Daily ITR Review (follow-up on missing and unusual reports)
- 6) Timeline Follow-back Questionnaire (since last visit)
- 7) Intention to Quit
- 8) Product Accountability Log
- 9) Compliance Review
- 10) End of Visit Evaluation

Procedures for Telehealth Week 3

A. Physiological Measures and Biomarker Samples:

- 1) Vital signs (blood pressure, heart rate) will be obtained while conducting the telehealth visit.
- 2) Carbon monoxide level will be obtained while conducting the video/phone visit.
- 3) Biological sample collection for analysis of nicotine and carcinogen metabolites collected at the prior to (first void urine) or at the telehealth visit (saliva) to be dropped off at the brief clinic or curbside visit.
- 4) Review cigarette butts collection from 24 hours prior to the visit. These spent filters will be dropped off at their brief clinic or curbside visit and analyzed for cigarette butt staining to inform intensity of smoking behavior.

B. Surveys – *link sent to participant to complete REDCap based survey:*

Biomarker Modifier Questionnaires:

- 1) Environmental Tobacco Smoke Questionnaire

Subjective Outcome Measures:

- 1) Minnesota Nicotine Withdrawal Scale (MNWS)
- 2) Questionnaire of Smoking Urges Brief Scale – Study Cigarette (QSU)
- 3) Respiratory Symptoms and Global Health Questionnaire
- 4) Modified Cigarette Evaluation Scale- Study Cigarette
- 5) Perceived Health Risk
- 6) Duke Sensory Questionnaire – Study Cigarette
- 7) BDI-II and or GAD7 will be administered for clinician to review if monitored for depression or anxiety.

C. Interviews - Research Assistant interviews participant and enters directly into REDCap:

- 1) COVID-19 Assessment
- 2) Health Changes and Menstrual Cycle Questionnaire
- 3) Adverse Events
- 4) Concomitant Medications
- 5) Daily ITR Review (follow-up on missing and unusual reports)
- 6) Timeline Follow-back Questionnaire (since last visit)
- 7) Intention to Quit
- 8) Product Accountability Log
- 9) Compliance Review

10) End of Visit Evaluation

Dispensing study product for Weeks 1-5

The participant will be provided their study cigarettes at the brief clinic or curbside visit. The subject will be allocated 150% of their baseline cigarettes per day. Allocating an additional 50% will provide cushion for possible late visits and/or compensatory smoking behavior. Subjects who return unopened packs of their study cigarette will continue to receive a \$2 credit per pack that will be paid out at the follow-up visit.

Procedures for Telehealth Week 6:

A. Physiological Measures and Biomarker Samples:

- 1) Self-reported weight
- 2) Vital signs (blood pressure, heart rate) will be obtained while conducting the telehealth visit.
- 3) Carbon monoxide level will be obtained while conducting the telehealth visit.
- 4) Biological samples will be collected prior to (first void urine) or at (saliva and optional collection of hair and blood spots) the telehealth visit to be dropped off at the brief clinic or curbside visit. Oral cells will be collected during the telehealth, in-person curbside or clinic visit.. Subjects will be instructed to brush teeth prior to collection.
 - a) Urine pregnancy tests [hCG detection] will be performed for female participants of childbearing potential to confirm eligibility.
- 5) Review cigarette butts collection from 24 hours prior to the visit. These spent filters will be dropped off at their brief clinic or curbside visit and analyzed for cigarette butt staining to inform intensity of smoking behavior.

B. Surveys – *link sent to participant to complete REDCap based survey:*

Biomarker Modifier Questionnaires:

- 1) Environmental Tobacco Smoke Questionnaire

Subjective Outcome Measures:

- 1) Minnesota Nicotine Withdrawal Scale (MNWS)
- 2) Questionnaire of Smoking Urges-Brief Scale – Study Cigarette (QSU)
- 3) Respiratory Symptoms and Global Health Questionnaire
- 4) Perceived Health Risks
- 5) Modified Cigarette Evaluation Scale – Study Cigarette
- 6) Cigarette Purchase Task – Study Cigarette
- 7) Nicotine Dependence Questionnaire
- 8) Duke Sensory Questionnaire – Study Cigarette
- 9) BDI-II and or GAD7 will be administered for clinician to review if monitored for depression or anxiety
- 10) Contemplation Ladder

- 11) Tobacco Policy Support Questionnaire
- 12) End of Study and Feasibility Questionnaire

C. Interviews - Research Assistant interviews participant and enters directly into REDCap:

- 1) COVID-19 Assessment
- 2) Health Changes and Menstrual Cycle Questionnaire
- 3) Adverse Events
- 4) Concomitant Medications
- 5) Daily ITR Review (follow-up on missing and unusual reports)
- 6) Timeline Follow-back Questionnaire (since last visit)
- 7) Intention to Quit
- 8) Product Accountability Log
- 9) Compliance Review
- 10) Smoking Cessation Counseling
- 11) End of Visit Evaluation

Dispensing study product

None

Cessation Materials at End of Intervention

At the end of the 6 week experimental period, subjects will be strongly encouraged to stop smoking and set a quit date and if possible, stop using all tobacco products. A treatment manual for cessation will be provided and subjects will be encouraged to call the state telephone quit line. Nicotine replacement products (1 box of choice of nicotine gum, lozenge or patches) will be provided to those setting a quit date.

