4.3 Participant Registration

[figure not shown]
Study registration will occur after the informed consent process is completed, consent form is signed and screening eligibility is confirmed. No study procedures will be conducted until after the consent form is signed, either electronically or a paper copy mailed or faxed to the clinic. To be enrolled in this study following screening, the participant must meet each criterion listed on the eligibility checklist based on the eligibility assessment documented in the case report record. Upon completion of the screening evaluation, and confirmation of eligibility, the study coordinator or designee will enroll the subject into REDCap.

5 Experimental Design:

Smokers will undergo a screening and then a three phase, 9 week experimental trial (Figure 1) with a one month follow-up at Week 10:

- 1) Phase 1 – Usual Brand Baseline: 1 week baseline assessment period of usual brand cigarette smoking;
- 2) Phase 2 – Study Cigarette Adaptation & Baseline Period: 2 week period allows the subject to adjust to the ventilated study cigarettes and obtain baseline data prior to randomization;
- 3) Phase 3 – Intervention: Randomization to either ventilated or unventilated study cigarettes for 6 weeks.

Figure 1:

[figure not shown]

Design

Subjects will be randomized at the end of Phase 2 (Visit 00) to one of the two experimental conditions (ventilated vs. unventilated cigarettes) for the 6-week intervention. An intervention

of six weeks was chosen because compensation is likely to stabilize by two weeks and biomarker levels should stabilize by six weeks.^{12,13}

Figure 2. Intervention Groups

Subjects will be informed of their assignment to ventilated cigarettes (cigarettes with similar ventilation as their usual brand) or unventilated cigarettes. As described above, study cigarettes are provided under single-blind conditions where subjects will not be informed of the filter design of the study cigarettes.

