5.8 Brief In-Person Clinic or Curbside Visits

A brief in-person visit will be scheduled following each of the telehealth visits. Depending on the circumstances, participants may have a brief in-person clinic or a curbside visit. If clinic visits are not optimal (due to COVID-19 prevalence/restrictions, use of public transportation or if a participant is not interested in being seen in the clinic) curbside contact will be arranged. The visits should be scheduled to occur as soon as possible after the telehealth visit. If the visit cannot be scheduled within 24 hours, a partial telehealth visit will occur to update the record. For the brief clinic or curbside pick-up, participants will be required to have a mask of either their own, sent by staff or provided one and told to wear it during the visit. Staff will wear PPE as required (optional if vaccinated. Any sample collection supplies, containers and other handouts will be provided at this time.

During the brief clinic or curbside visit, subjects will drop off the appropriate biosamples, cigarette butts and collect the week's supply of study cigarettes and return empty packs. If there have been device issues with the vitals or CO monitors, they can troubleshoot at this visit.

Biosamples to be returned at this visit:

- 1) First morning void urine collection (Weeks 92, 00, 3, 6, Early Terminating (ET) if applicable)
- 2) Saliva sample obtained for nicotine metabolite ratio-NMR (Week 92)
- 3) Saliva sample for TNEs (Weeks 92, 00, 3, 6, ET if applicable).
- 4) Blood spot (Weeks 00, 6); this collection is optional.
- 5) Hair sample (Week 6); this collection is optional.
- 6) Cigarette butt collection (Weeks 00, 3, 6)

Procedures to be conducted at this visit:

- 1) Oral cells will be collected during the telehealth, in-person curbside or clinic visit. Subjects will be instructed to brush teeth prior to arrival at the visit.
- 2) Inhalation measures (Weeks 00 and 6) will be conducted on a subset of subjects.

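### As written, the visit 00 inhalation baseline is taken after the randomization script is read, and the plan does not settle whether the visit 00 surveys come before it

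*Combined protocol and SAP*

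**What the plan says.** Four parts of the protocol bear on the order of events at visit 00.

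- **Section 5.6, opening of the visit 00 procedures.** Disclosure is named first and the measures second: "subjects will be informed that they have been randomized to either ventilated or unventilated study cigarettes. Subjects will complete several measures". The sentence then refers the reader to the list below it.
- **Section 5.6, visit 00 list.** Part A covers physiological measures and samples, part B the surveys, and part C the interviews. The script is item 7 of part C: "Randomization to either ventilated or unventilated cigarettes - Read appropriate script". The part B surveys are self-completed ("link sent to participant to complete REDCap based survey") and include the mCES, Perceived Health Risk and the dependence questionnaire. At the clinic or curbside contact, "the participant will be provided their randomized study cigarettes (ventilated or unventilated").
- **Section 5.8.** "A brief in-person visit will be scheduled following each of the telehealth visits". Among the procedures for that in-person contact: "Inhalation measures (Weeks 00 and 6) will be conducted on a subset of subjects".
- **Section 5, Experimental Design, text with Figure 2.** One sentence says "Subjects will be informed of their assignment to ventilated cigarettes" or to unventilated ones. The next describes a single blind under which "subjects will not be informed of the filter design of the study cigarettes".

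Section 10.1 makes visit 00 the starting point for the secondary inhalation endpoint and for the FTND, mCES and Perceived Health Risk endpoints.

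**The concern.** A baseline should be measured before participants can react to their allocation. How deeply someone inhales in an observed session, and how they rate a cigarette's harm or appeal, can both change once they believe they know which product they will get. If the visit 00 value is taken after that point, any immediate reaction becomes part of the baseline. The comparison from visit 00 to Week 6 then subtracts it, wholly or in part.

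This matters here because the trial itself expects arm differences in smoking intensity and perceived harm (section 1.2). Section 10.2 also reads a 95% interval for the FTND group coefficient that contains zero as showing no difference, so a bias toward zero would not be a safe error.

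**Working it through.** **Step 1. Inhalation: put the sections in time order.**

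1. Telehealth call for visit 00. The script is read during the interview (section 5.6, part C, item 7).
2. In-person contact. It is scheduled after the call, and section 5.8 allows for a gap of more than 24 hours.
3. At that contact, the subset has its Week 00 inhalation session (section 5.8) and the randomized cigarettes are handed over (section 5.6).

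Following the plan as written, every inhalation baseline comes after the script. Within step 3, the documents do not say whether the session precedes the handover or which cigarette is smoked in it. Section 5.2 describes the device and says the spent filter is kept, but settles neither point.

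**Step 2. Surveys: the order is unresolved.** The opening sentence of the visit 00 procedures puts disclosure first. The list puts all surveys (part B) before the script (part C). No text says the surveys must be submitted before the script is read, and they are completed from a link. Section 11 (Data Integrity) leaves the order of measures to a visit checklist that is not part of the documents.

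**Step 3. What is clearly before the script.**

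- Baseline NNAL comes from a first-void urine taken before the call (section 5.6).
- Baseline CPD is a Phase 2 mean (section 10.2).
- The cigarette butts cover the 24 hours before visit 00 (section 5.6).

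**Step 4. Direction of bias.** Let D be the true Week 6 arm difference, d the arm difference in the visit 00 mean caused by the script, and r the correlation between visit 00 and Week 6, with D and d in SD units.

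- Change-score contrast: D − d.
- Baseline-adjusted contrast: D − r × d.

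A d with the same sign as D and smaller than it shrinks a real effect. A d of opposite sign inflates it. If D = 0, a spurious difference appears.

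**Step 5. Scale, for illustration only.** The plan has no figure to reproduce on this point. It gives no shift, no correlation and no subset size, so d, r and n = 20 per group are assumptions. With D = 0, a two-sided 5% test and a normal approximation:

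- SE (change) = √(2/n) × √(2(1 − r))
- SE (adjusted) = √(2/n) × √(1 − r²)

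At n = 20, √(2/20) = 0.316. For d = 0.2 and r = 0.5:

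- Change: SE = 0.316 × 1.000 = 0.316, bias/SE = 0.20/0.316 = 0.63, rejection rate 9.7%.
- Adjusted: bias = 0.5 × 0.2 = 0.10, SE = 0.316 × 0.866 = 0.274, bias/SE = 0.37, rejection rate 6.5%.

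| Assumed d (SD) | Change score, r = 0.3 to 0.7 | Baseline-adjusted, r = 0.3 to 0.7 |
|---|---|---|
| 0.1 | 5.8% to 6.9% | 5.1% to 6.1% |
| 0.2 | 8.3% to 12.9% | 5.5% to 9.5% |
| 0.3 | 12.6% to 23.2% | 6.0% to 15.3% |
| 0.5 | 26.7% to 53.2% | 7.9% to 34.1% |

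Small shifts do little harm in a group of this size. Larger ones would matter.

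**The case against.** There are four points on the other side.

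**The opening sentence is only a summary.** It defers to the list, which puts the surveys before the script. The Procedure Table also marks the visit 00 mCES, Perceived Health Risk and dependence forms with a V, apparently for the ventilated cigarette just smoked in Phase 2, and the unseen checklist may fix the order. This stands. A reader might infer that the subjective baselines are taken after disclosure; the documents show only that nothing explicitly prevents it.

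**The arm may not be disclosed at all.** If the single-blind sentence in section 5 governs, the script reveals nothing about filter design and the mechanism largely fails. This stands as a condition on the whole point. It does not dispose of it, because the sentence just before it says the opposite and the list calls for an appropriate script, which suggests wording that differs by arm.

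**An immediate effect is speculative.** No document estimates one, and the FTND, which asks about consumption and dependence, is an unlikely candidate for a sudden change. This stands, and it is why no size is claimed. Inhalation in an observed session is harder to dismiss.

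**Moving the script is more than a reordering.** The in-person contact may be curbside and may come a day or more later. This has some force if allocation and script move for everyone. It has little if only the reading of the script moves, and only for the inhalation subset.

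**Conclusion.** The point holds for the inhalation endpoint: the plan as written places its baseline after the script for the whole subset. Whether that introduces bias depends on the script revealing the arm, which section 5 leaves contradictory, and on participants reacting to it. The size is unknown; the table in the working rests entirely on assumed values.

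For the mCES, Perceived Health Risk and FTND, the order is open, so this is a gap to close and not a demonstrated fault.

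Two stronger readings should be resisted. One is that the bias runs toward no difference; the algebra shows it can go either way. The other is that the trial's main conclusions are at risk; the baselines for NNAL, CPD and the butt-based intensity measure all precede the script. This is a minor point about secondary endpoints, worth making because the correction is cheap.

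**What to change.** 1. Reconcile section 5 (Figure 2 text), the opening sentence and list for visit 00 in section 5.6, and section 5.8. State what the script tells the participant and when it is read.
2. Require the visit 00 surveys to be submitted before the script is read.
3. For the inhalation subset, read the script at the in-person visit, after the inhalation session and before the assigned cigarettes are handed over. State that the session uses the Phase 2 ventilated study cigarette.
4. Staff may generate the allocation earlier to prepare product. Only disclosure needs to move.
5. For data already collected, use survey and session time stamps to flag post-script baselines and run a sensitivity analysis without them. For inhalation this may mean comparing Week 6 values alone, since the whole subset may be flagged. For the mCES, the visit 91 value on the ventilated study cigarette can serve as baseline. Perceived Health Risk was not measured at visit 91.

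The cost is a small change in visit workflow for the subset, with no extra visit or staff.
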